9.4 DATA SOURCES

We will utilize medical and pharmacy claim records for COPD patients included in the database (previously named).

Page 32 of 47

c38026921-01

Proprietary confidential information © 2022 Boehringer Ingelheim International GmbH or one or more of its affiliated companies

9.5 STUDY SIZE

Considering the study design being non-interventional study with existing data, retrospective, new user design and treatments being: Stiolto Respimat (active treatment) vs. Trelegy Ellipta (comparator), primary endpoint of time to first exacerbation (moderate/severe) and COPD population being maintenance treatment naïve, we didn't find any such study that exactly matches these criteria in literature.

We looked at two retrospective, observational, non-interventional studies in the literature. Suissa et al published in Chest (CHEST 2020; 157(4):846-855) a real-world study of COPD treatment, the triple combination of LAMA, LABA, and ICS inhalers and compared its effectiveness to combining LAMA and LABA inhalers in preventing COPD exacerbations.²³ Suissa et al had a sample size of ~2000 patients on LAMA and LABA.²³ They reported that the adjusted hazard ratio (HR) of a COPD exacerbation associated with LAMA-LABA-ICS initiation compared with LAMA-LABA initiation was 0.97 (95% CI, 0.87-1.08). For patients with blood eosinophil counts > 6%, the HR was 0.66 (95% CI, 0.46- 0.94). For patients with two or more prior exacerbations, it was 0.83 (95% CI, 0.70-0.98). ²⁹ The incidence of severe pneumonia requiring hospitalization was increased with LAMA-LABA-ICS initiation (HR, 1.46; 95% CI, 1.03-2.06). ²⁹ The second study, by Palli et al compared health plan-paid costs, COPD exacerbations, and pneumonia diagnoses among patients newly treated with a LAMA + LABA regimen composed of tiotropium (TIO) + olodaterol (OLO) in a fixed-dose combination inhaler (TIO + OLO) or TT in a U.S. Medicare Advantage Part D insured population.²⁴ This study was published in Journal of Managed Care & Specialty Pharmacy 2020 26:10, 1363-1374 and had a sample size of ~1500 patients on Stiolto.³⁰ Palli et al reported longer time to first severe COPD exacerbation (P = 0.020) and first pneumonia diagnosis (P = 0.002) for TIO + OLO versus TT and a lower percentage of TIO + OLO patients experiencing these events (severe COPD exacerbation: 9.0% vs. 16.1%; pneumonia: 14.5% vs. 19.3%).³⁰

Feasibility Assessment: Using database we identified 15,538 and 35,686 patients who initiated first line treatment with Stiolto or Trelegy, respectively, between 15^{th} September 2017 and 31^{st} March 2020. These patients had 12-months of baseline with both medical and pharmacy coverage. After applying the inclusion/ exclusion criteria the sample size is reduced to 3996 patients in the Stiolto group and 5121 in the Trelegy group and post PSM our final sample size is 3018 in each group, which gives sufficient power when compared to earlier studies (Suissa et al (~2000 patients with LAMA-LABA) and Palli et (~1500 patients per cohort) as mentioned above). Based on these two studies from the literature and the feasibility numbers for the current study we are confident that we will have enough patients to ensure \geq 80% power.

Proprietary confidential information © 2022 Boehringer Ingelheim International GmbH or one or more of its affiliated companies

9.6 DATA MANAGEMENT

All established security and confidentiality procedures will be observed by BI and/or personnel who are assigned appropriate access to the data. Enrolment data, medical claims, and prescription claims will be accessed from the administrative claims' dataset. The analyses will be performed on limited data sets that are void of

member protected health information and all results were shared in aggregate form only.

9.7 DATA ANALYSIS

Summary measures will include standard descriptive statistics (e.g., mean, standard deviation, median and range for continuous variables; counts and percentages for categorical variables). However, for any baseline characteristics with significant differences (Standardized differences (SD) greater than 0.10 (10%)) after PSM matching, these characteristics will be included as covariates in the regression models, or we will develop interaction terms to match on or discontinue the study if major channeling (SD>10%) is observed. Basically, a two-step approach: The first step will be to characterize the patients after PS matching to see whether balance can be achieved (based on SD) and at least 2000 patients from the Stiolto cohort can be matched with at least 2000 patients in the Trelegy cohort before proceeding to the second step of doing the comparative analysis. Sensitivity analyses may be performed on a select set of covariates considered to be prognostic factors. In the event of study discontinuation, partial results (all analysis leading up to and including PSM) will be provided in a final report.

A Cox proportional hazards models will be used on the time to first COPD exacerbation with treatment as a covariate. Comparisons will be made between treatment cohorts using HR and will be presented with associated 95% CI. To account for variable lengths of follow-up observation time, population annualized results will be provided (annualized costs [e.g., Sum of total costs/Sum of total follow-up patient years for each cohort]). The annualized cost may be modelled as dependent variable in a Generalized Linear Model with treatment cohort as a covariate and the follow-up patient years as an offset for each cohort.

Comparisons will be made between treatment cohorts and will be presented with associated 95% CI. Additionally, descriptive techniques that account for the length of observation time measure will be used appropriately. Per patient per month calculations will not be performed because of bias concerns. Appropriate tests comparing the Stiolto cohort and the Trelegy cohort (e.g., standardized differences, McNamara's tests, paired t-tests, sign tests) will be used based on the distribution of the measure. Patients not matched will be excluded from the post-match analysis.

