The following outcomes will be measured in the baseline and follow-up periods. The baseline period will include claims occurring on the index date, except for the index medication claims, which will be included in the follow-up period.

- All-cause health care resource utilization: Indicator variables and counts of physician office visits, hospital outpatient visits, ED visits, "other" (non-inpatient) visits, inpatient stays, and pharmacy claims will be created. Other medical visits are a residual category that includes, but is not limited to, services rendered at independent laboratories, assisted living facilities, and by home health providers. An indicator variable will be created to identify inpatient stays with an acute stay during the inpatient stay, the time to first inpatient stay will also be captured. The time to first inpatient stay, the time to first eD visit during follow-up will be captured.
- COPD and/or pneumonia-related health care resource utilization: This utilization will be calculated analogously to all-cause utilization, but restricted to medical claims with a diagnosis for COPD and/or pneumonia, in any position (Appendix 1) and pharmacy claims for a COPD-related treatment (Appendix 2), including COPD-guideline recommended antibiotics (Appendix 3).

- COPD-related health care resource utilization: This utilization will be calculated analogously to all-cause utilization, but restricted to medical claims with a diagnosis for COPD in any position (Appendix 1) and pharmacy claims for a COPD-related treatment (Appendix 2), including COPD-guideline recommended antibiotics (Appendix 3)
- Pneumonia-related health care resource utilization: This utilization will be calculated analogously to all-cause utilization but restricted to medical claims with a diagnosis for pneumonia in any position (Appendix 1).
- COPD or pneumonia-attributable health care resource utilization: This utilization will be calculated analogously to all-cause utilization, but restricted to medical claims with a diagnosis for COPD or pneumonia in the primary position or a diagnosis for acute respiratory failure in the primary position and a diagnosis for COPD or pneumonia in a non-primary position (Appendix 1) and pharmacy claims for a COPD-related treatment (Appendix 2), including COPD-guideline recommended antibiotics (Appendix 3)

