- All-cause health care costs (insurer + patient paid amounts): Health care costs will be computed from the payer and patient perspective together. This is the actual amount paid to the provider by the health plan plus the patient co-pay and/or coinsurance amounts, rather than an estimated cost. Total costs will be calculated and presented as the combined pharmacy costs and medical costs. Medical costs will be presented and will include sub-categories of physician office costs, hospital outpatient costs, emergency services costs, inpatient costs, and other costs.
 - Costs will be adjusted to 2019 dollars using the medical care component of the Consumer Price Index (CPI) to reflect inflation between the date of the claim and 2019.²² The final report will include additional columns with the latest available 2020 mid-year CPI adjustment applied to costs for scaling the results as needed.²²
 - Costs from other payers may be important, particularly for studies involving older patients dually eligible for commercial and Medicare coverage. In consultation with this study will NOT incorporate the amounts estimated to be paid by other payers for a total paid or allowable amount.²³
- COPD and/or pneumonia-related health care costs (insurer + patient paid amounts): These costs will be calculated analogously to the all-cause costs, but restricted to medical diagnosis claims with а for COPD. pneumonia, or acute bronchitis/bronchiolitis in any position (Appendix 1) and pharmacy claims for a COPDrelated treatment (Appendix 2), including COPD-guideline recommended antibiotics (Appendix 3).
- COPD-related health care costs (insurer + patient paid amounts): These costs will be calculated analogously to the all-cause costs, but restricted to medical claims with a diagnosis for COPD in any position (Appendix 1) and pharmacy claims for a COPD-related treatment (Appendix 2), including COPD-guideline recommended antibiotics (Appendix 3).

Proprietary confidential information © 2022 Boehringer Ingelheim International GmbH or one or more of its affiliated companies

- Pneumonia-related health care costs (insurer + patient paid amounts): These costs will be calculated analogously to the all-cause costs but restricted to medical claims with a diagnosis for pneumonia in any position (Appendix 1).

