9.3.3 Covariates

Patient characteristics at baseline will be assessed for Stiolto and Trelegy users overall and stratified by history of exacerbation.

The covariates included in the Propensity Score Matching (PSM) will include all the below covariates including the ones defined during the 12-month pre-index baseline period and chronic comorbid conditions.

- Gender
- Age group (years, categorical and a continuous variable)
- Calendar year of cohort entry
- Region
- Insurance type (e.g., Commercial, Medicare)
- Season of index date (winter, spring, summer, fall)

Additional characteristics that will be defined during the 12-month pre-index baseline period:

- Previous acute COPD exacerbation (measured both overall and in the 30 days prior to cohort entry), categorized as 0, 1, or ≥2.
 - All exacerbations (Moderate+Severe)
 - Hospitalizations (Severe)
- Use of other respiratory drugs in the 12-month pre-index period:
 - Short-acting beta-agonists
 - Short-acting Anticholinergics
 - Methylxanthines
 - o LAMA
 - o LABA

Proprietary confidential information © 2022 Boehringer Ingelheim International GmbH or one or more of its affiliated companies

- o ICS
- o ICS/LABA
- Use of antibiotics commonly prescribed for a respiratory condition (e.g., azithromycin)
- Use of OCS
- Oxygen Use
- Pulmonary Rehabilitation

Chronic comorbidities were defined using diagnoses identified during all available data prior to the index date, and included

- Quan-Charlson Comorbidity Index score/individual comorbidities
- Cardiovascular disease
- Diabetes
- Renal failure
- GERD
- Arthritis
- Osteoporosis
- Cancer (excluding basal cell carcinoma)
- Baseline pneumonia diagnosis
- Baseline acute bronchitis diagnosis
- Diagnosis of dyspnea during baseline identified using ICD 9 786.0x and ICD 10 R06.0x
- Diagnosis of obesity during baseline identified using ICD 9 278.xx and ICD 10 E66.xx
- Diagnosis of alcohol dependence during baseline identified using ICD 9 303.xx, 305.0x and ICD 10 F10.xx
- Smoking dependence during baseline identified using ICD 9 305.1 and ICD 10 F17.xx
- Tobacco use or cessation counselling*

*We anticipate limited capture of lifestyle variables known to be risk factors and potential confounders, including obesity, smoking status, and excessive alcohol consumption.

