9.7.1 Main analysis

Analyses will be presented comparing Stiolto vs Trelegy overall after PSM matching and stratified as follows if the sample size allows (at least 15% in each strata):

• Low history of exacerbation: 0 inpatient (i.e., severe exacerbations) and 0-1 outpatient events (i.e., moderate exacerbations)

Proprietary confidential information © 2022 Boehringer Ingelheim International GmbH or one or more of its affiliated companies

• High history of exacerbation: ≥1 inpatient (i.e., severe exacerbations) or ≥2 outpatient events (includes ED)

We will describe the formation of the study cohort. Patient characteristics at baseline in patients treated with Stiolto and patients treated with Trelegy will be assessed separately using standard descriptive statistics.

Propensity scores including both pre-specified and data-derived variables will be then calculated. Balance of patient characteristics between the cohorts will be described before and after propensity score application and compared using standardized differences. For each Stiolto patient, a Trelegy patient with the closest available propensity score will be selected. Nearest neighbor matching method with a caliper of 0.2 will be utilized. Standardized differences greater than 0.10 (10%) will be taken to indicate imbalance, and these variables will also be included in outcome models, categorized as appropriate.

For the analysis of the primary objective, a Cox proportional hazard regression model will be used to perform an as-treated analysis that assesses the effect of first line maintenance medication with Stiolto versus the first line maintenance medication with Trelegy on the time to first COPD exacerbation. This estimates the HR of a COPD exacerbation associated with Stiolto use relative to Trelegy use, along with 95% CI. Based on the days' supply post index date, allowing a grace period of 45 days following the end of days' supply to account for intermittent use.

Stratified analyses will be using the same approach as the main analysis. Calculation of propensity scores will be repeated within the subset of the cohort with available results to create weighted populations suitable for these stratified analyses.

The analysis of the secondary objective related to the risk of pneumonia will also be assessed using Cox proportional hazard regression models with an as-treated approach, like that of the primary analysis.

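### The planned cost model omits baseline cost, which the study already measures, and so gives up precision and leaves small baseline cost differences unadjusted

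*Combined protocol and SAP*

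**What the plan says.** Section 8 makes differences in utilization and cost between the two cohorts a secondary objective. Section 9.3 introduces those measures with "The following outcomes will be measured in the baseline and follow-up periods", and the list that follows covers all-cause, COPD-related, pneumonia-related and attributable utilization and costs. Section 9.3.1 sets the baseline window at 12 months. Claims for the index drug itself count in follow-up.

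The only cost model is in Section 9.7: "The annualized cost may be modelled as dependent variable in a Generalized Linear Model with treatment cohort as a covariate", together with "the follow-up patient years as an offset for each cohort". The model is optional, and its family and link are not stated.

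Three other provisions bear on adjustment:

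- **Imbalance rule.** For characteristics whose standardized difference is above 0.10 after matching, Section 9.7 says "these characteristics will be included as covariates in the regression models", though it also offers interaction terms or stopping the study as alternatives. Section 9.7.1 says of such variables that "these variables will also be included in outcome models".
- **Sensitivity analyses.** Section 9.7 adds: "Sensitivity analyses may be performed on a select set of covariates considered to be prognostic factors".
- **Propensity score.** Section 9.3.3 says "The covariates included in the Propensity Score Matching (PSM) will include all the below covariates". The list includes prior exacerbations, hospitalizations, respiratory drugs and comorbidities, but not baseline cost or total utilization. Section 9.7.1 also allows unnamed data-derived variables.

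**The concern.** Each patient has a pre-index value of the same measure that is later compared between cohorts. Where the two values are correlated, putting the first in the model for the second removes part of the patient-to-patient variation from the treatment contrast. That gain exists even when the cohorts are perfectly balanced, and no section plans to take it. With a balanced match, treatment cohort is the only covariate.

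The imbalance rule does not fill the gap. It acts only above 0.10, so a smaller residual difference in baseline cost stays in the contrast. It may also never be applied to baseline cost: Section 9.3 lists costs among the outcomes, separately from the clinical and patient characteristics, and no section says that baseline cost goes into the balance check.

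At stake are the width of the confidence interval for a secondary objective and, if some baseline cost difference survives matching, the location of the estimate.

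**Working it through.** **Inputs.**

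- Matched sample: 3018 per group (Section 9.5). The minimum to proceed is 2000 per group (Section 9.7).
- Two-sided 0.05, inferred from the 95% confidence intervals.
- Correlation rho between baseline and follow-up cost: not in the documents, assumed 0.2 to 0.7.
- Standard deviation (SD) of cost: not in the documents, so results are in SD units.

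**The plan's own figure.** Section 9.5 claims at least 80% power for the study in general. It gives no cost difference and no cost SD, so there is no cost figure to reproduce. Below, 80% is only a reference point.

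**Precision.** Adjusting for baseline cost multiplies the residual variance by (1 − rho²) and the standard error (SE) by √(1 − rho²).

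- Unadjusted SE = √(2/3018) = 0.0257 SD.
- Detectable difference at 80% power = (1.960 + 0.842) × 0.0257 = 0.0721 SD, multiplied by √(1 − rho²) after adjustment.
- Equivalent sample per group = 3018/(1 − rho²).
- Power at the unadjusted detectable difference = Φ(2.802/√(1 − rho²) − 1.960).

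| Assumed rho | SE factor | Fall in SE | Detectable difference (SD) | Equivalent n per group | Power at 0.0721 SD |
|---|---|---|---|---|---|
| 0 | 1.000 | 0% | 0.0721 | 3018 | 80.0% |
| 0.2 | 0.980 | 2% | 0.0707 | 3144 | 81.6% |
| 0.3 | 0.954 | 5% | 0.0688 | 3316 | 83.6% |
| 0.5 | 0.866 | 13% | 0.0625 | 4024 | 89.9% |
| 0.7 | 0.714 | 29% | 0.0515 | 5918 | 97.5% |

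The SE factors do not depend on sample size. At 2000 per group and rho 0.5, the detectable difference falls from 0.0886 to 0.0767 SD.

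**Does this carry over to a generalized linear model?** The formula belongs to linear models. As a check, log-normal costs (log-SD 1.2, assumed) were simulated for 3018 per group and analysed by a gamma model with log link, with and without log baseline cost, in 300 runs. The SE ratios were 0.92, 0.81 and 0.64 at log-scale correlations of 0.3, 0.5 and 0.7. The gain runs in the same direction and is somewhat larger than the linear formula gives. These correlations are on the log scale, and equal follow-up was assumed.

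**Differences that the 0.10 rule leaves in place.** A baseline cost difference of exactly 0.10 SD does not trigger adjustment. It shifts the follow-up contrast by 0.10 × rho SD.

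- rho 0.3: 0.030/0.0257 = 1.2 SE, giving a false-positive rate of about 21% instead of 5%.
- rho 0.5: 0.050/0.0257 = 1.9 SE, giving about 49%.

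This is the edge of what the rule tolerates, not an expected value. Treating the groups as independent, a chance difference has an SD of 0.0257, so 0.10 is 0.10/0.0257 = 3.9 of those. A difference that large would have to be a systematic residue of the match, and the documents give no data showing one.

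**The case against.** The strongest reply is that the plan is not a treatment-only analysis. The model carries a follow-up offset. The imbalance rule in Section 9.7 covers any baseline characteristic and is not confined to the propensity list. Data-derived variables may enter the propensity score, and sensitivity analyses on prognostic factors are allowed. This stands as a description: treatment is the sole covariate only by default, and a baseline cost difference above 0.10 might be picked up. It does not meet the point. The rule yields no precision when the match is balanced and does nothing at or below 0.10, and the other provisions are optional or name no variable.

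A second reply is that rho may be low. Patients used no maintenance inhaler for six months before index, while the index drug is charged to follow-up. On-treatment follow-up can be short, which makes annualized cost noisy. One correlation is also unlikely to fit all-cause, COPD-related and pneumonia-related cost. All of this stands, and at rho 0.2 to 0.3 the loss is only 2% to 5% of the SE.

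Third, pairs are matched on prior exacerbations, hospitalizations, drugs and comorbidities, which probably overlap with baseline cost, and the paired tests in Section 9.7 may use some of that. This also stands, so the percentages above lean high.

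Finally, cost is secondary, mainly reported descriptively, and the model is optional. That limits the importance of the point, but a stated comparative objective still needs a defined comparison.

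**Conclusion.** The point holds in a limited form. Baseline cost is measured but not prespecified in the cost model, and nothing guarantees that it is checked for balance. The plan forgoes a reduction of about 2% to 29% in the SE of the cost contrast (13% at rho 0.5), assuming rho between 0.2 and 0.7 and no gain already made by matching. It also leaves baseline cost differences of 0.10 or less unadjusted.

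Two stronger conclusions might be inferred, and the documents support neither. One is that baseline cost is the best predictor of later cost: no correlation is reported for it or for any other variable. The other is that the cost comparison is biased because baseline cost is missing from the propensity list: the documents show no baseline cost difference, and the matched variables may already balance it. Leaving out a prognostic covariate costs efficiency and does not by itself invalidate the comparison.

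**What to change.** In Section 9.7, replace the optional cost model with a prespecified one, along these lines:

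> Each cost measure will be compared between the matched cohorts with a generalized linear model, which is the inferential analysis for cost. Covariates are treatment cohort and log(1 + the baseline 12-month value of the same measure). For measures that are often zero at baseline, such as pneumonia-related cost, an indicator of zero baseline cost is added.

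So that the sentence can be carried out, it should also name the family, the link and the variance estimator for matched pairs, and say whether the response is total cost with an offset or cost already annualized.

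List baseline cost in the post-match balance table, so that the 0.10 rule clearly covers it. Use the corresponding baseline count for utilization only if those counts are modelled, since Section 9.7.1 describes them without a model. Keep summed cost over summed patient-years as a description.

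The baseline values are already being built, so the change needs no new data. It costs some wording and slightly more analysis work, and it brings little if the correlation proves low.

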9.3.1 Exposures

Patients will be assigned to one of the following mutually exclusive study cohorts based on the index pharmacy claim: Stiolto Respimat or Trelegy Ellipta. Exposure measures will be based on pharmacy dispensing of the two medications under study, namely Stiolto Respimat or Trelegy Ellipta, over a follow-up period, beginning the index date and lasting up to one year from index date. Discontinuation for index medication will be defined as a gap in index medication of \geq 45 days (sensitivity analysis with \geq 30 days can be included) following the runout of days' supply (discontinuation date = runout prior to the gap in therapy). Switch in index medication will be defined as a pharmacy fill for \geq 30 consecutive days of a non-index maintenance medication (switch date = first date of the new treatment regimen). Switch includes any other change in use of index medication by active ingredient, inclusive of a change to a different combination therapy (ICS/LABA FDC, different LAMA/LABA or LAMA/LABA/ICS FDC) change from a FDC to a free form combination therapy with mono LAMA plus mono LABA, or mono ICS plus mono LABA, or mono LAMA plus mono LABA plus mono ICS or a change to a monotherapy.

Individuals in the study cohort will be followed from the index date until the earliest of the date of a switch in treatment, addition of an ICS for the Stiolto Respimat group, discontinuation of the index COPD maintenance treatment, the end of the study period, or the end of continuous health plan eligibility. Main analyses will be further limited to the first 12 months after index date, with sensitivity analyses considering all available data.

All patients will be required to be continuously enrolled in the health plan for a minimum of 12 months. The 12 months prior to and including the index date (index date – 364 through index date) will be used to assess baseline characteristics. The period starting the day after the index date, up to a maximum of 12 months duration (index date +1 through index date +365) will be used to assess exacerbation, pneumonia, HCRU and cost outcomes. Patients will be censored at the earliest of the following: discontinuation of the index medication (Stiolto or Trelegy), switch to a non-index medication, disenrollment from the health plan, 12-months following the index date, or the end of the study period.

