9.3.2.2 Secondary Outcome(s)

The secondary outcome is time to first hospitalization for community-acquired pneumonia (serious pneumonia). Pneumonia was defined using ICD-9-CM diagnoses 481.x-486.x; 487.0, 507.x, 507.0, 507.1, 507.8, 510.0, 510.9, 511.0, 513.0, 514.x, 517.1, 519.8, 530.84, and ICD-10 diagnosis codes J10.0; J11.0; J12-J18; J22; J69; J85.0; J85.1; J86. This definition has been previously used in COPD. ^{27,28}

- COPD and/or pneumonia related HCRU (including acute inpatient stays and their length of stay, emergency department visits, ambulatory [Physician office visits, hospital outpatient visits], and other medical visits)
- COPD-related HCRU
- Pneumonia-related HCRU
- COPD-attributable HCRU
- All-cause HCRU

HCRU is defined as total inpatient, emergency department, and outpatient care episodes. Estimates will be presented both overall and for COPD and/or pneumonia-related care, defined as claims where a diagnosis of COPD or pneumonia is present. Medications used, defined as total number of distinct medication subclasses dispensed (e.g., 4-digit level of the Generic Product Identifier) and total number of dispensing for medications per year. COPDrelated medication utilization included all COPD medications, OCS, and guidelinerecommended antibiotics

Annual HCRU costs (including costs paid by the patient, health plan, and any third party via coordination of benefits) will be then calculated as total costs, medical costs, pharmacy costs, ambulatory costs, ED costs, inpatient costs, and other costs. Costs were defined as related to COPD if the claim has a diagnosis for COPD in any position or is a pharmacy claim for a medication used to treat COPD. The sum of all costs from all care settings and pharmacy dispensing will be assessed overall, for COPD and/or pneumonia-related care.

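### As worded in 9.7, the optional cost GLM divides cost by patient-years and then offsets by patient-years again, so on a log link follow-up is adjusted for twice

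*Combined protocol and SAP*

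**What the plan says.** Section 9.7 deals with unequal follow-up by annualizing at cohort level: "Sum of total costs/Sum of total follow-up patient years for each cohort". The next sentence makes that annualized cost, optionally, the "dependent variable in a Generalized Linear Model with treatment cohort as a covariate and the follow-up patient years as an offset for each cohort". It gives no link, distribution, transformation of the offset or effect measure. The same section promises 95% CIs for cohort comparisons and adds: "Per patient per month calculations will not be performed because of bias concerns". Nothing elsewhere says that the modelled outcome is undivided cost.

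Follow-up is on treatment and at most one year. The last paragraph of 9.3.1 states: "Patients will be censored at the earliest of the following: discontinuation of the index medication (Stiolto or Trelegy), switch to a non-index medication", followed by disenrollment, 12 months and the end of the study period. An earlier paragraph of 9.3.1 also ends follow-up when an ICS is added, for the Stiolto group only; the last paragraph's list omits this. The documents report no follow-up by arm.

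On payers, 9.3 counts insurer plus patient payments and says "this study will NOT incorporate the amounts estimated to be paid by other payers". Section 9.3.2.2 describes annual costs as "including costs paid by the patient, health plan, and any third party via coordination of benefits".

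**The concern.** An offset of log patient-years turns a model for total cost into a model for cost per year. Here the named outcome is already cost per year, so the offset divides by time again. Any difference between the arms in time on treatment then enters the cost ratio.

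This GLM is the only regression the plan names for costs, and cost comparison is a secondary objective. If it were run as written on a log link, its ratio could disagree with the crude annualized costs in the same report, and a reader could not tell which to believe.

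**Working it through.** The plan states no figure for this model, so there is none to reproduce. The check is algebra, with illustrative numbers.

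**Inputs.** From 9.7: outcome y = C/T (cost over follow-up years), offset T, treatment as covariate. From 9.5: 3018 patients per group after matching. Assumed: log link, log(T) offset, mean follow-up by arm, and an annual cost rate r that does not depend on T, equal in both arms (true ratio 1.00).

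**Literal model, patient level.** log E[y] = b0 + b1·trt + log T. Since y = C/T, this says E[C] = T² × exp(b0 + b1·trt), whereas a constant annual rate means E[C] = T × r.

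- Poisson-type variance: the estimating equation in each arm is Σ(y − T·e^b) = 0, so e^b = Σy/ΣT, which is r/mean(T) in expectation. The fitted ratio is the true ratio × mean(T) Trelegy / mean(T) Stiolto.
- Gamma variance: the equation is Σ(y/(T·e^b) − 1) = 0, so e^b = mean(y/T), which is r × mean(1/T) in expectation. The fitted ratio is the true ratio × mean(1/T) Stiolto / mean(1/T) Trelegy.

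The gamma column below assumes 30 days plus an exponential time, cut at one year.

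| Mean follow-up, Stiolto vs Trelegy (years) | Poisson-type | Gamma |
|---|---|---|
| 0.50 vs 0.50 | 0.50/0.50 = 1.000 | 1.000 |
| 0.48 vs 0.50 | 0.50/0.48 = 1.042 | 1.038 |
| 0.45 vs 0.50 | 0.50/0.45 = 1.111 | 1.098 |
| 0.40 vs 0.50 | 0.50/0.40 = 1.250 | 1.208 |
| 0.50 vs 0.45 | 0.45/0.50 = 0.900 | 0.911 |
| 0.50 vs 0.40 | 0.40/0.50 = 0.800 | 0.828 |

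**The gamma column is not a bound.** At 0.40 vs 0.50, a minimum follow-up of 1, 7, 30 or 60 days gives 1.30, 1.26, 1.21 or 1.18. Simulated fits with beta-distributed follow-up (20 data sets, 3018 per arm) gave 1.346.

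**Equal means do not rescue the gamma model.** For T ~ Beta(a, b), mean(1/T) = (a+b−1)/(a−1). Beta(2,2) gives 3/1 = 3.00 and Beta(4,4) gives 7/3 = 2.33; both have mean 0.50, yet the ratio is 1.29. Beta(1.5,1.5) against Beta(3,3) gives 4.0/2.5 = 1.60.

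**When the ratio cancels, the level is still wrong.** With r = 20,000 dollars (assumed) and mean follow-up 0.50 in both arms, the Poisson-type model's cost at one year of follow-up is 20,000/0.50 = 40,000.

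**Other readings.**

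- Cohort-level outcome: two observations and two parameters, so no CI.
- Unlogged years on a log link: 1.045 to 1.056 at 0.45 vs 0.50.
- Identity link: years are subtracted from dollars per year. This has no meaning, but shifts the cost difference by at most 0.50 − 0.40 = 0.10 dollars in the scenarios above.

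**Corrected model.** With outcome C and offset log(T), the Poisson-type equation Σ(C − T·e^b) = 0 gives e^b = ΣC/ΣT, which is the plan's own annualized cost. In the beta simulations this model returned 0.995 at 0.45 vs 0.50 and 0.992 at 0.40 vs 0.50, where the literal one returned 1.104 and 1.243.

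**The case against.** The strongest reply is that the sentence is shorthand. Naming patient-years as an offset is the usual way to obtain an annual rate from total cost, and the authors may have meant just that. This is plausible, and it is why the point is limited to the text as written. But the text names annualized cost as the outcome, directly after defining it as a quotient, and a programmer would implement the named variable.

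Nor does the cost comparison depend on this model. It is optional, 9.7.1 plans descriptive cost results, and 9.7 lists paired tests. All of that stands.

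A reader might infer several stronger things that the documents do not support:

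- *That the study's cost results will be biased.* This needs the optional model to be run, a log link that the plan does not state, and annualized rather than total cost as the outcome. The crude annualized costs are untouched.
- *That the bias has a known size or direction.* No follow-up by arm is given, and it may be equal. Nor does the Stiolto-only ICS rule in 9.3.1 prove a difference: the switch definition there, at least 30 days of a non-index maintenance drug, may already capture much of it in either arm. It shows only that equality is not assured.
- *That equal mean follow-up removes the problem.* This is true for the between-arm ratio under a Poisson-type variance, not under gamma.
- *That the payer definitions flatly contradict each other.* Section 9.3 excludes estimated other-payer amounts; 9.3.2.2 may mean recorded coordination-of-benefits payments. Neither section draws that distinction.

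**Conclusion.** The wording is wrong as it stands: on a log link with a log(years) offset, the stated outcome and offset adjust for follow-up twice. Under a Poisson-type variance, and if annual cost does not depend on follow-up, the cost ratio is off by the inverse ratio of mean follow-up: 11% for assumed means of 0.45 vs 0.50 years, and nothing if the means are equal. Under gamma the condition is equal mean(1/follow-up), and the size depends on the whole follow-up distribution. The link, the follow-up figures and their distributions are assumptions.

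The consequence is confined to an optional model for a secondary objective; the primary Cox analysis is unaffected. The payer wording is a separate, minor clarification. It changes dollar totals, and changes the ratio only if third-party shares differ by arm.

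**What to change.** In 9.7, replace the GLM sentence with:

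> Total on-treatment cost per patient may be modelled in a GLM with log link, treatment cohort as covariate and log(follow-up years) as offset, and the cost ratio reported with a 95% CI that accounts for matched pairs.

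State the variance function too. Quasi-Poisson is suitable: without further covariates it reproduces the plan's crude annualized cost ratio, and it allows zero costs. Zeros will arise for pneumonia-related costs, which are "calculated analogously to the all-cause costs but restricted to medical claims with a diagnosis for pneumonia in any position". Another variance may be used if justified. A gamma model does not admit zeros and targets the mean of individual annualized costs, not the cohort quotient that the plan defines.

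Pair-clustered standard errors, or a bootstrap that resamples pairs, would serve for the CI.

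Separately, give one payer definition in 9.3 and 9.3.2.2, saying whether recorded coordination-of-benefits payments count, and reconcile the two lists in 9.3.1 of what ends follow-up.

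The cost is a few lines of text and no extra data. The CI may be slightly wider. In one simulation (3018 per arm, gamma cost with shape 0.5, shared pair frailty with variance 0.25) the limits were the ratio divided and multiplied by 1.10 with pair clustering. Model-based errors gave 1.09 but covered only 90–92%.
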